Study visits will typically occur in the subjects home, unless they prefer to come to the office. 1. Recruitment and Enrollment: Following a routine office visit, or upon self-referral and review of records, the patient will be scheduled for a baseline visit with the coordinator, if eligible. Additional pre-screening may occur with the subject via phone. 2. Baseline visit: The study coordinator will finish confirming eligibility via pre-screening questions (if not already completed prior to the visit). Once eligibility is confirmed, subjects will provide consent. Additionally, the subjects will fill out the following questionnaires: Preference: Belief in Medication Questionnaire (BMQ, gold standard), Bidirectional Visual Analogue Preference scale Physical activity: Accelerometer (gold standard), Self-reported questionnaires (IPAQ, CHAMPS) Neurocognitive measures: Questionnaires (Minicog, Falls risk) Urinary: Questionnaires (OABq-SF, UDI-6) Quality of Life: SF-12 Bowels: Questionnaires (Birmingham) Short Physical Performance Testing will be performed with oversight from trained personnel. The study coordinator will provide subjects with accelerometers and instructions for wearing the accelerometer. The monitor will be retrieved from the patient by a study coordinator or investigator a week later. 3. Intervention: All subjects will receive a 90-day supply of open label fesoterodine 4 mg per day, which they will start 1 week after the baseline visit. After 2 weeks, dose may be increased to 8 mg over the telephone based on symptom report. Change of prescription to another anti-cholinergic may occur during the study period, if determined necessary by the physician. See full criteria in previous intervention section above. 4. 8 week follow up visit: At this visit, the patient will complete the following self-administered physical activity, urinary symptoms, adherence, pill count, and neurocognitive instruments and tests: Physical activity: Accelerometer (gold standard), Self-reported questionnaires (IPAQ, CHAMPS) Neurocognitive measures: Questionnaires (Minicog, Falls

risk), Short Physical Performance Battery Urinary: Questionnaires (OABq-SF, UDI-6) Bowels: Questionnaires (Birmingham) Quality of Life: SF-12 Adherence: Questionnaires (BMQ follow up, MASRI), pill count Patient Global Index of Improvement (PGI-I) form The study coordinator will again provide subjects with accelerometers and instructions for wearing the accelerometer, one week prior to the 8 week visit. The monitor will be retrieved from the patient by a study coordinator or investigator at the 8 week visit. Instrument and Testing Schedule BASELINE VISIT: Preference: Belief in Medication Questionnaire (BMQ, gold standard), Bidirectional Visual Analogue Preference scale Physical activity: Accelerometer (gold standard), Self-reported questionnaires (IPAQ, CHAMPS) Neurocognitive measures: Questionnaires (Mini cog, Falls risk), Short Physical Performance Testing Urinary: Questionnaires (OABq-SF, UDI-6) Quality of Life: SF-12 Bowels: Questionnaires (Birmingham) 8 WEEK FOLLOW-UP VISIT: Physical activity: Accelerometer (gold standard), Self-reported questionnaires (IPAQ, CHAMPS) Neurocognitive measures: Questionnaires (Mini Cog, Falls risk), Short Physical Performance Testing Urinary: Questionnaires (OABq-SF, UDI-6) Bowels: Questionnaires (Birmingham) Quality of Life: SF-12 Adherence: Questionnaires (BMQ follow up, MASRI), pill count Patient Global Index of Improvement (PGI-I) form

The following documents are currently attached to this item:

There are no documents attached for this item.

Deception

Does your project use deception?

No

International Research

Are you conducting research outside of the United States?

No

Analysis Plan

Analysis Plan Specific Aim 1 and 2: We will evaluate physical activity, adherence, and neurocognitive function before and after treatment to examine changes from baseline to 8 weeks in subjects with and without preference for medication. Concurrent validity, the relationship of the instrument to other similar evaluations, will be measured by comparing IPAQ, and CHAMPS scores to accelerometer data at baseline using the Spearman correlation coefficient and the intraclass correlation coefficient. Specifically, we will compare energy expenditure in MET*min/week (IPAQ) or MET*hour/week (CHAMPS) to that measured by the Actigraph accelerometer over the course of a week. For preference, we will compare subjects scores as indicated on the bidirectional scale to their necessity-harm differential as calculated by the Belief Screen of the BMQ using Spearman correlation coefficient. Contingency analyses tables will be used to determine the sensitivity and specificity of the bidirectional preference scale and the necessity-harm differential (as calculated on the Belief Screen) that best discriminates between those with preference for medication and those without. Discriminant validity, the ability to distinguish between populations, will be determined by comparing mean differences in energy expenditure for each physical activity instrument between responders and non-responders to anticholinergic medication as defined by the PGI-I. We will compare total MET*min/week (IPAQ) or MET*hour/week (CHAMPS), as well as energy spent in sedentary and moderate-to-vigorous physical activities (CHAMPS) between responders and non-responders using Wilcoxon rank sum test. For preference, we will compare the BMQ Belief necessity-harm differential and bidirectional preference scale score using Wilcoxon rank sum test. Responsiveness, the ability of the instruments to detect clinically meaningful change, will be assessed. First, pretreatment energy expenditure and preference will be compared with post-treatment activity and preference scores, respectively, using the t-test. Next, effect size (change in mean score/SD of baseline) and standardized response mean (change in mean score/SD of the change) will be assessed. For both, values of 0.50.7 will be considered moderate responsiveness; 0.81, good; and 1, excellent. We will measure minimum clinically important difference (MCID); specifically, the smallest change in physical activity associated with clinically meaningful change in global rating scale (mean change in energy expenditure in subjects indicating a little better or greater in the global rating scale). Specific Aim 3: We will compare within subject change in physical activity from baseline to 8 weeks using the paired t-test. Improvement in physical activity will be defined as 15% increase in energy expenditure as compared to baseline. The effect of age, comorbidities, baseline activity, severity of cognitive impairment, BMI on physical activity will be examined using regression analysis. We will also compare change in activity, proportion of subjects

showing improvement in activity, adherence (80% or greater, as measured by pill count and MASRI), response to medication (PGI-I), overall quality of life (SF-12), neurocognitive and balance function (MMSE and Berg Balance Scale scores, respectively), and urinary symptoms (OABq-SF score) in adults expressing preference for medication to those expressing no preference. The effect of preference will be measured using regression analysis, with adjustment for baseline physical activity, Charlson co-morbidity index, age, and BMI.

The following documents are currently attached to this item:

There are no documents attached for this item.

Data confidentiality

- Paper-based records will be kept in a secure location and only be accessible to personnel involved in the study.
- Computer-based files will only be made available to personnel involved in the study through the use of access privileges and passwords.

Prior to access to any study-related information, personnel will be required to sign statements agreeing to protect the security and confidentiality of identifiable information.

- Wherever feasible, identifiers will be removed from study-related information.

A Certificate of Confidentiality will be obtained, because the research could place the subject at risk of criminal or civil liability or cause damage to the subject's financial standing, employability, or liability.

A waiver of documentation of consent is being requested, because the only link between the subject and the study would be the consent document and the primary risk is a breach of confidentiality. (This is not an option for FDA-regulated research.)

Precautions are in place to ensure the data is secure by using passwords and encryption, because the research involves web-based surveys.

Audio and/or video recordings will be transcribed and then destroyed to eliminate audible identification of subjects.

Subject Confidentiality

Extensive efforts will be made to ensure and maintain participant confidentiality. Data from patients will be recorded on data collection forms, which will be associated with a Subject ID number only. The patient name, medical record numbers, or other identifiers will not be present on the data collection forms themselves. The Subject ID number will be composed by the sequential ordering of participants. A log book will be kept in for data management purposes to match Subject ID number with patient medical record numbers if chart review is needed for missing data. This will also be maintained in a secure and locked filing system at all times. Any additional source documentation that may associate the patient and PHI to data (such as consent forms) will also be kept in a secure and locked filing system at all times. Additionally, any data collection forms will also be kept in a separate secure and locked filing system at all times. All data will be stored in a REDCap database using their assigned Subject ID number. This is protected by a secure system requiring log-in and password. The data from the accelerometers is downloaded using the secure software that comes with the Actigraph device, known as Actilife. This data is then analyzed by the software, and converted into Excel files. These Excel files will be password-protected.

Sensitive Research Information*

Does this research involve collection of sensitive information about the subjects that should be excluded from the electronic medical record?

No

Subject Privacy

Privacy refers to the person's desire to control access of others to themselves. Privacy concerns people, whereas confidentiality concerns data. Describe the strategies to protect privacy giving consideration to the following: The degree to which privacy can be expected in the proposed research and the safeguards that will be put into place to respect those boundaries. The methods used to identify and contact potential participants. The settings in which an individual will be interacting with an investigator. The

privacy guidelines developed by relevant professions, professional associations and scholarly disciplines (e.g., psychiatry, genetic counseling, oral history, anthropology, psychology). Study visits will typically occur in subjects' homes, allowing for complete privacy. Any telephone calls required to contact patients will be performed in a private manner.

Data Disclosure

Will the data be disclosed to anyone who is not listed under Personnel?

No.

Data Protection*

- Name**
- Street address, city, county, precinct, zip code, and equivalent geocodes**
- All elements of dates (except year) for dates directly related to an individual and all ages over 89**
- Telephone and fax number**
- Electronic mail addresses**
- Social security numbers**
- Medical record numbers**
- Health plan ID numbers**
- Account numbers**
- Certificate/license numbers**
- Vehicle identifiers and serial numbers, including license plate numbers**
- Device identifiers/serial numbers**
- Web addresses (URLs)**
- Internet IP addresses**
- Biometric identifiers, incl. finger and voice prints**
- Full face photographic images and any comparable images**
- Any other unique identifying number, characteristic, or code**
- None**

Does your research request both a waiver of HIPAA authorization for collection of patient information and involve providing Protected Health Information ("PHI") that is classified as a "limited data set" (city/town/state/zip code, dates except year, ages less than 90 or aggregate report for over 90) to a recipient outside of the University of Pennsylvania covered entity?

No

Tissue Specimens Obtained as Part of Research*

Are Tissue Specimens being obtained for research?

No

Tissue Specimens - Collected during regular care*

Will tissue specimens be collected during regulator clinical care (for treatment or diagnosis)?

No

Tissue Specimens - otherwise discarded*

Would specimens otherwise be discarded?

No

Tissue Specimens - publicly available*

Will tissue specimens be publicly available?

No

Tissue Specimens - Collected as part of research protocol*

Will tissue specimens be collected as part of the research protocol?

No

Tissue Specimens - Banking of blood, tissue etc. for future use*

Does research involve banking of blood, tissue, etc. for future use?

No

Genetic testing

If genetic testing is involved, describe the nature of the tests, including if the testing is predictive or exploratory in nature. If predictive, please describe plan for disclosing results to subjects and provision of genetic counseling. Describe how subject confidentiality will be protected Note: If no genetic testing is to be obtained, write: "Not applicable."

Not applicable

Consent

1. Consent Process

Overview

Informed consent will be obtained by the study coordinator after the patient is identified as a potential recruit for the study. The subjects will have as much time as needed to consider participation between informing the prospective participant and obtaining consent. The patient may also choose to withdraw from the study at any time. Investigators will emphasize that participation (or lack of participation) in the study: 1) not influence their evaluation, care, or treatment 2) is completely voluntary 3) does not involve any financial compensation 4) may be terminated at any time. Layman terms will be used by those obtaining the consent. The consent will be written at a 6th grade reading level. All questions will be answered to the patient's satisfaction and understanding before informed consent is obtained.

Children and Adolescents

Not applicable

Adult Subjects Not Competent to Give Consent

All adult subjects must be competent to give informed consent to be eligible for inclusion into this study.

2. Waiver of Consent

Waiver or Alteration of Informed Consent*

No Waiver Requested

Minimal Risk***Impact on Subject Rights and Welfare*****Waiver Essential to Research*****Additional Information to Subjects****Written Statement of Research***

No

If no written statement will be provided, please provide justification**The following documents are currently attached to this item:**

There are no documents attached for this item.

Risk / Benefit

Potential Study Risks

Physical Risks: Because this is a trial involving the use of fesoterodine, there are possible physical risks to the patients secondary to the medication in use and the clinical outcome. However, this is minimal since fesoterodine is 1) a FDA-approved medication available in the United States and regularly used for treatment of overactive bladder, and 2) has relatively few and mild side effects. Risks include: 10%: Gastrointestinal: Xerostomia (19% to 35%; dose related) 1% to 10%: - Central nervous system: Insomnia (1%) - Dermatological: Rash (1%) - Gastrointestinal: Constipation (4% to 6%), dyspepsia (2%), nausea (1% to 2%), abdominal pain (1%) - Genitourinary: Urinary tract infection (3% to 4%), dysuria (1% to 2%), urinary retention (1%) - Hepatic: ALT increased (1%), GGT increased (1%) - Neuromuscular & skeletal: Back pain (1% to 2%) - Ocular: Dry eyes (1% to 4%) - Respiratory: Upper respiratory tract infection (2% to 3%), cough (1% to 2%), dry throat (1% to 2%) - Miscellaneous: Peripheral edema (1%) - 1% (Limited to important or life-threatening): Angina, angioedema, diverticulitis, gastroenteritis, heat prostration, hypersensitivity reactions, irritable bowel syndrome, QTc prolongation Additionally, we will be starting with the lowest dose of fesoterodine available and monitoring all adverse effects. In a meta-analysis of randomized controlled trials with fesoterodine, any adverse effects were usually categorized as mild to moderate, and was most commonly associated with dry mouth and constipation (mild adverse effects). (Wyndaele 2014) Additionally, amongst elderly patients taking fesoterodine, no trials have shown changes in mean MMSE score, computer-based cognitive test battery (CogState), or Rey Auditory Verbal Learning Test scores, even in the vulnerable elderly (patients at high risk for functional decline or death within 2 years). (Chapple 2015) There is a potential for falls during the SPPB testing, but this will be conducted with the oversight of trained personnel, and subjects are encouraged to vocalize concerns and stop if there are any potential for falling during the course of the testing. Loss of confidentiality: Any study in which personal health information (PHI) is collected has the potential risk of loss of confidentiality. However, extensive efforts will be made to ensure and maintain security of PHI and maintain participant confidentiality. Patients will be identified and screened by physician investigators at each site involved in patient care in their offices. The patient will be brought into a private room before discussing the study and enrollment with the patient in the privacy of a private room. During the study, interactions with patients will involve questionnaires and tests which will be conducted in private rooms in physicians' offices. Data from patients will be recorded on data collection forms, which will be associated with a Subject ID number only. The patient name, medical record numbers, or other identifiers will not be present on the data collection forms themselves. The Subject ID number will be composed by the sequential ordering of participants. A log book will be kept in for data management purposes to match Subject ID number with patient medical record numbers if chart review is needed for missing data. This will also be maintained in a secure and locked filing system at all times. Any additional source documentation that may associate the patient and PHI to data (such as consent forms) will also be kept in a secure and locked filing system at all times. Additionally, any data collection forms will also be kept in a separate secure and locked filing system at all times. One year after the study has been completed, any forms with patient identifiers (such as logs and consents) will be destroyed. All data will be logged into a REDCap database using their assigned Subject ID number. This is secure and password protected. The data from the accelerometers is downloaded using the secure software that comes with the Actigraph device, known as Actilife. This data is then analyzed by the software, and converted into Excel files. These Excel files will be password-protected. There are no psychological, social, economic, monetary, or legal risks to this study. Wyndaele JJ, Schneider T, MacDiarmid S, Scholfield D, Arumi D. Flexible dosing with fesoterodine 4 and 8 mg: a systematic review of data from clinical trials. *Int J Clin Pract.* 2014 Jul;68(7):830-40. doi: 10.1111/ijcp.12425. Chapple C, Oelke M, Kaplan SA, Scholfield D, Arumi D, Wagg AS. Fesoterodine Clinical Efficacy and Safety for the Treatment of Overactive Bladder in Relation to Patient Profiles: A Systematic Review. *Curr Med Res Opin.* 2015 Mar 23:1-78. [Epub ahead of print]

Potential Study Benefits

Potential benefits to the individual subject include improvement of overactive bladder symptoms from fesoterodine use. Additionally, by validating and measuring responsiveness in physical activity, neurocognitive, and balance instruments, we will be able to increase generalizability of these instruments and validate them for use in future clinical trials. Lastly, this will provide preliminary data on the impact of treatment preference and anti-cholinergic medications on physical activity and falls risk in older adults with overactive bladder, potentially improving quality of life and decreasing life-

threatening consequences of falls in the elderly.

Alternatives to Participation (optional)

Patients are not required to participate in the study. Alternatives would include trying other medical and surgical treatments for overactive bladder without questionnaires, measurements of daily activity with an activity monitor, or other testing.

Data and Safety Monitoring

The Principal Investigator will be responsible to monitoring safety, privacy, and data integrity. This study contains low risks, as fesoterodine is a first-line drug already used in daily in clinical practice for treatment of overactive bladder. Study progress will also be reviewed by the PI. Review of the rate of subject accrual, adherence to inclusion/exclusion criteria will occur to assure that participants meet the eligibility criteria. There will be ongoing collection of data on adverse events and compliance to the treatment protocol throughout the study by research staff.

The following documents are currently attached to this item:

There are no documents attached for this item.

Risk / Benefit Assessment

The benefits of this treatment outweigh the risks. As discussed before, there is the potential for risk of physical harm and loss of confidentiality as part of participation in this study. However, the risk of physical harm is minimal secondary to the minor adverse effects of fesoterodine, and minimization of the dose administered in this study. Additionally, these medications are already being used as first-line medication in the treatment of overactive bladder in the urogynecology/urology fields. The loss of confidentiality will be minimized by careful and secure management of all paper and electronic documentation of patient data. Additionally, participation in questionnaires and neurocognitive/balance testing could help clinicians discover patients at risk of falls and refer subjects for other medical evaluation as needed. Participation in this study could potentially benefit the patient by decreasing overactive bladder symptoms and improving quality of life. If this trial is successful, benefits to elderly patients could result in improved quality of life, decreased urinary symptoms, increased safety, and decreased risk of the morbidity and mortality associated with falls.

General Attachments

The following documents are currently attached to this item:

There are no documents attached for this item.

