(Tzefos 2009, AHRP reference guide) Additionally, fesoterodine has been compared to tolterodine, and may show greater efficacy. (Tzefos 2009) In fact, fesoterodine tends to have low incidence of dry mouth, and moderate incidence of constipation compared to other anti-muscarinics, making it a well-tolerated and appropriate first choice for most patients.(Ellsworth 2014) Low CNS penetration may also potentiate fewer CNS side effects.(Ellsworth2014) Additionally, our previously presented data on the potential positive effects of anticholinergic medication on physical activity was collected using fesoterodine, so there is a precedent for using this anticholinergic in a study examining changes in activity and sedentary behavior. Therefore, fesoterodine, the drug used in this study, is an appropriate medication for routine and standard care of overactive bladder. Fesoterodine is being supplied by Pfizer for the use of this study. As part of routine clinical care at the urogynecology clinics of the University of Pennsylvania Health System, all patients receive a pelvic exam, measurement of post-void residual by bladder ultrasound, and administration of four urinary questionnaires as part of evaluation of urinary symptoms. The OABq-SF and the UDI-6 will be used to screen patients. Inclusion Criteria: adults aged 65 or older, urinary urgency of quite a bit severity or more on the Overactive Bladder Questionnaire-Short Form (OABq-SF),50 who are eligible for pharmacologic therapy for overactive bladder Exclusion Criteria: predominant stress incontinence (on UDI-6), current/recent use (6 m) or contraindication to anti-cholinergic medication, severe voiding difficulties, men on 5-alpha reductase inhibitors, severe neurologic disease, recent anti-incontinence or prolapse surgery, other urinary tract conditions such as calculus or recurrent UTI. Recruitment/Retention Experience: The urogynecology/urology clinics of the Hospital of University of Pennsylvania are high volume referral clinics staffed by four urogynecologists and one urologist. We see 125 female and 50 male patients with OAB per month with eligibility:participation ratio of 1.5:1 in clinical trials.42, 48, 51 In recent trials, 50% of recruited adults were Caucasian and 45% African-American. We anticipate that the female:male ratio will be 2:1. Recruitment : Pre-screening will occur at a patients routine visit, or via chart review following clinical care. If a patient appears to be eligible, they will be referred to the study coordinator to schedule a baseline visit. Patients of urogynecology or other referring geriatrics/urology/primary care practices may also self-refer for participation, as long as their medical records are available for eligibility determination. Baseline visit: At this visit, the trained coordinator will obtain informed consent, administer physical activity and other questionnaires (see Instrument and Testing Schedule below). Routine pre-treatment counseling on medical treatment, as well as counseling on additional non-medical (biofeedback, behavioral strategies, pelvic floor muscle training) and interventional treatments (neuromodulation), will also be provided. Then the coordinator will administer the Preference instrument on a bidirectional scale with 0 being undecided, and either extreme (5 or -5) being a strong preference for that particular treatment. The Short Physical Performance Battery (SPPB) test will also be performed with the oversight of trained personnel for safety. Accelerometers and instructions for wearing the accelerometer will be provided at that time. The monitor will be retrieved from the patient by a study coordinator or investigator 1 week later. Intervention: All subjects (irrespective of preference) will receive a 90-day supply of open label fesoterodine 4 mg per day. They will start medication 1 week after the baseline visit. After 4 weeks of treatment, dose may be increased to 8 mg over the telephone based on symptom report. This dosing regimen is direct alignment with clinical care. Change of prescription to another anti-cholinergic may occur during the study period, if determined necessary by the physician. Criteria that would warrant stopping fesoterodine include: - inability to tolerate common side effects, including dry mouth, dry eyes, and constipation - lack of satisfactory urinary symptom control on the highest dose of fesoterodine - immediate withdrawal in case of life-threatening side effects (uncommon, including angina, angioedema, diverticulitis, gastroenteritis, heat prostration, hypersensitivity reactions, irritable bowel syndrome, QT prolongation) Once withdrawn from fesoterodine, managing physicians would use their clinical judgment to switch the patient to another anti-cholinergic medication or switch to another class of medication (beta 3 agonist, or mirabegron). These patients would continue to be followed until after the 8 week follow-up visit, as the statistical plan will involve intention-to-treat analysis. The patients will continue to participate in the 8 week follow-up visit (including questionnaires and SPPB), regardless of whether or not they were switched to another medication. All adults will receive printed educational material on fluid modification, behavioral strategies, and Kegel exercises. 8 week follow up visit: One week prior, the study coordinator will once again provide subjects with accelerometers and instructions for wearing the accelerometer. At the 8 week visit, the patient will again complete self-administered physical activity, urinary symptoms, adherence, pill count, and neurocognitive instruments and tests with the oversight of a trained investigator (see Instrument and Testing Schedule below). The monitor will be retrieved from the patient by a study coordinator or investigator at the 8 week follow up visit. Instrument and Testing Schedule BASELINE VISIT: Urinary questionnaires (OABq-SF, UDI-6) Preference: Belief in Medication Questionnaire (BMQ), Bidirectional Visual Analogue Preference scale Physical activity:

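### The baseline preference score, the exposure in Aims 2 and 3, is not concealed from staff who oversee the staff-observed secondary outcomes

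*Combined protocol and SAP*

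**What the plan says.** Two sections describe how preference is collected.

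- **Study Design, Baseline visit.** The coordinator obtains consent and gives the questionnaires. After counselling on treatment options, "Then the coordinator will administer the Preference instrument on a bidirectional scale".
- **Study Procedures, Procedures.** At the same visit "the subjects will fill out the following questionnaires: Preference: Belief in Medication Questionnaire (BMQ, gold standard), Bidirectional Visual Analogue Preference scale". On location: "Study visits will typically occur in the subjects home, unless they prefer to come to the office".

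For the observed tests, Study Design says of baseline: "The Short Physical Performance Battery (SPPB) test will also be performed with the oversight of trained personnel for safety". At the 8 week follow up visit the patient completes instruments described as self-administered, including the pill count and "neurocognitive instruments and tests with the oversight of a trained investigator".

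The Analysis Plan for Aim 3 compares adherence (pill count and MASRI), cognition, balance, symptoms and activity "in adults expressing preference for medication to those expressing no preference". No cut-off for preference is fixed. Contingency tables are to find the values of the scale and of the Belief in Medication Questionnaire (BMQ) differential "that best discriminates between those with preference for medication and those without".

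**The concern.** Preference is the exposure. If the person scoring a balance or cognitive test, or counting pills, knows how strongly the subject favoured medication, the scoring or handling can drift with that knowledge. The Objectives make the team's expectations explicit: those who prefer medication should adhere better and should not differ on neurocognitive testing. Drift towards the first expectation could look like an effect of preference on adherence. Drift towards the second could hide a real neurocognitive difference.

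The open-label drug is unavoidable in this design, and so is the subject's own awareness of the preference. Staff access to the score is avoidable, and the plan is silent on it.

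**Working it through.** The plan gives no figure that bears on this point, so the check is a side-by-side reading, followed by an illustration that rests on assumptions.

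**Who collects the exposure.** Study Design names the coordinator as giving the scale; Procedures has the subject complete it. The two can be reconciled, but as written they leave open who sees the answer.

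**Who could see it.** The Subject Confidentiality and Potential Study Risks sections provide coded forms, locked storage and a password-protected database. These protect identity. None of them restricts which study staff may read the preference score. The Resources section names a project coordinator as the funded support staff, so overlap between the person collecting preference and the visit staff is plausible but not stated.

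**Which outcomes are exposed.**

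- *Staff-observed by nature:* the Short Physical Performance Battery (SPPB) and Mini-Cog in the testing schedule, or the MMSE and Berg scale named instead in the Analysis Plan; possibly the pill count.
- *Little affected:* the primary outcome (accelerometer and self-reported activity), and MASRI, PGI-I, OABq-SF and SF-12, which are patient-reported.

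**What staff would know.** With no cut-off fixed, staff could know a score but not a final group. The BMQ, called the gold standard for preference in Procedures, is collected at both visits and gives similar information.

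**Illustration only.** From the Accrual section: 80 enrolled, 15% loss, 50% with preference, 56% adherence in unselected subjects, two-tailed alpha 0.05 (stated for Aim 3). Evaluable per group: 80 × 0.85 / 2 = 34. The size of the tilt is assumed; the documents give none.

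- *Continuous score.* For a spurious group difference of d standard deviations with no true difference, the rejection rate is Φ(−1.96 + d/√(2/34)) + Φ(−1.96 − d/√(2/34)), where √(2/34) = 0.2425. For d = 0.1, 0.2 and 0.3 this gives 7.0%, 13.1% and 23.6%.
- *Pill-count adherence.* With 56% overall and a spurious difference b split equally between the groups, se₀ = √(2 × 0.56 × 0.44/34) = 0.120 and se₁ = √[(p₁(1−p₁) + p₂(1−p₂))/34]. The rate is 1 − Φ((1.96·se₀ − b)/se₁) + Φ((−1.96·se₀ − b)/se₁). For b = 5, 10 and 15 points this gives 7.0%, 13.1% and 23.6%.

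With no tilt the rate is 5%. These figures show sensitivity to an assumption and do not estimate bias in this study.

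**The case against.** Several stronger readings are tempting, and the documents do not support them.

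- *A reader might infer that staff ask for the preference face to face and record it.* The same paragraph has the coordinator administer other questionnaires that are plainly self-reported, the instrument is a visual analogue scale, and Procedures has subjects fill it out. In-person visits make spoken questioning possible, but it is stated nowhere. For the same reason, a claim that answers are pushed towards medication is conjecture.
- *A reader might infer that the week-8 assessor knows the group.* The overseer is described only as a trained investigator. Nothing says this is the coordinator or someone holding the score, and the group is not yet defined.
- *A reader might take an inflated false-positive rate as the consequence.* The tilt is assumed. For neurocognitive testing the team expects no difference, so expectation would pull towards the null and would not create false positives. A tilt that is constant across visits would also cancel in change scores. On the SPPB, if scored in whole points, a mean tilt of 0.5 would need about 0.5 × 34 = 17 subjects in one group over-scored by a point; nothing in the documents suggests this.
- *A reader might expect concealing the scale to abolish the problem.* If the BMQ stays visible, it gives away much the same information, and subjects can speak. Sealing a paper form until week 8 could also leave a blank exposure undiscovered until after treatment.

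What stands after these points is narrow. Concealment of the exposure is unaddressed, the two sections on collecting it differ, and staff-observed results enter the comparison by preference.

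**Conclusion.** The point holds as an avoidable risk in secondary, staff-observed measures: the SPPB or balance test, the cognitive test and possibly the pill count. The plan neither conceals the preference score nor says who may see it, and its two accounts of how the scale is completed need reconciling. The primary outcome and the other self-reported outcomes are little affected by what staff know.

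The size of any bias cannot be given from the documents, and its direction may differ by outcome. The conclusion assumes that some visit staff could see the score, which the plan leaves open but does not state. In an open-label single cohort meant partly to yield preliminary data, this is a desirable improvement, not a flaw that threatens the study.

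**What to change.** 1. Reconcile the Study Design and Procedures sections: the subject completes the bidirectional scale alone. Treat the BMQ in the same way, since it also indicates preference.
2. Collect both on a REDCap form with required fields, hidden from visit staff. Alternatively, use an envelope checked for completeness by existing staff who do not run that subject's tests.
3. Release the scores only after that subject's week-8 tests and pill count have been entered.
4. State who may see the scores and when.

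This reduces the risk but does not remove it. The cost is a wording change and a permission setting or envelope handling; no change to sample size, visits or treatment follows. There is a small risk of incomplete forms, which required fields or the independent check should limit, and subjects may still state their preference aloud. The envelope route needs someone other than the assessor to hold the form, and the documents do not show whether staffing allows that; the REDCap route avoids the question.
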